6.3.8 PPE usage

The following PPE usage of subjects included in the study will be descriptively summarized for HCWs with and without COVID-19 infection (see Table 8.2.9 in the appendix):

A stacked bar chart will be used to display PPE usage during the follow-up period. The x-axis will be dates of survey responses and the stacked bars will be grouped by yes/no (corresponding to PPE use at specific dates). This will be done separately for HCWs infected with COVID-19 and those uninfected. The stacked bar charts can be used to compare PPE use among infected/uninfected HCWs over time. This will be done for the four types of PPE (eg. masks, eye protection, gowns, gloves).

- PPE used in workplace since first known contact with COVID-19 patients
 - Mask (Yes always; Yes not always; No)
 - Type of Mask (N95 Respirator Mask; Other)
 - Eye Protection (Yes always; Yes not always; No)

- Gown (Yes always; Yes not always; No)
- Gloves (Yes always; Yes not always; No)
- The number of PPEs used as “yes always” among mask, eye protection, gown, gloves will also be summarized: none, one, two, three, all four

For HCWs with COVID-19 at entry: responses to the baseline survey will be used

For HCWs with COVID-19 at follow-up: overall PPE usage over the entire follow-up time available in the data cut. In addition, overall PPE usage in the 2 or 4 weeks (TBD) prior to COVID-19 infection date will be described.

For HCWs with no COVID-19 infection at any time: overall PPE usage over the entire follow-up time available in the data cut. In addition, overall PPE usage in the 2 or 4 weeks (TBD) prior to the data cut date will be described.

Overall PPE usage will be defined as the following from multiple weekly surveys being considered as above:

Responses seen in all weekly surveys being considered	Overall PPE usage
Yes always	Yes always
Yes always Yes not always	Yes not always
Yes always No	Yes not always
Yes always Yes not always No	Yes not always
Yes not always	Yes not always
Yes not always No	Yes not always
No	No

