3.4 Follow-up period

The HCWs will be followed up for 12 weeks upon enrollment in the study.

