5 Determination of Sample Size

The targeted sample size of approximately 10,000 HCWs assumes that 20% of the study population are non-exposed to potential prophylactic treatments, with a baseline risk of SARS-CoV-2 infection in the study period of 10% (for unexposed: not treated with potential prophylactic treatment). A total of N=10,000 allows for 80% power to identify an effect size of Relative Risk = 0.78.

If these sample sizes are not reached with respect the study population being exposed/non-exposed to potential prophylactic treatments, the relative risk may be detected with lower power or it may not be statistically significant. However, the secondary objectives can still be examined.

6 Statistical analysis

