6.1 Overview

All statistical analyses will be conducted using R (version 1.3.1093), unless otherwise specified.

For all descriptive analyses, categorical variables will be summarized by number of observations and percentage (%). Percentages will be rounded to one decimal place and will be based on available observations (known values), unless otherwise specified. Continuous variables will be summarized using descriptive statistics (n, mean, with standard deviation; minimum, first quartile, median, third quartile,

and maximum). Outliers will be included in descriptions as part of presenting ranges and percentiles (25th and 75th). The mean and SD will be rounded to one decimal place.

All statistical tests will be two-sided and at 5% level of significance.

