Time-varying Covariates	Others in household exposed to COVID-19 infected individuals, Others in household showing symptoms of COVID-19, Others in household diagnosed with COVID-19, Number of COVID-19 infected patients exposed to, Direct care to COVID-19 patients, Face-to-face contact of COVID-19 patients, Present when aerosol generating procedures performed, Mask usage, Gown usage, Eye protection usage, Glove usage
-------------------------	--

Note: The necessity to create composite variables or collapse categories within variables will be determined upon the completion of the descriptive analyses. A correlation analysis will be completed to assess the level of correlation between variables, if a high level of correlation is found only one of the variables will be included as a covariate in the models.

A Cox model with mixed effects can be formulated as $h_i(t) = h_0(t) \exp(\mathbf{X}_i B + \alpha_j)$, where α_j denotes the random effect associated with the j -th cluster. The random effect can be thought of as a random intercept that modifies the linear predictor, while the shared frailty term has a multiplicative effect on the baseline hazard function: $h_i(t) = h_0(t) \exp(\alpha_j) \exp(\mathbf{X}_j B)^3$.

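### The all-or-nothing PPE label in SAP 6.3.8 depends on how many weekly surveys are counted, and can mask or dilute a real PPE association in the descriptive comparison

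*SAP*

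**What the plan says.** SAP 6.3.8 describes PPE use for workers with and without infection and reduces several weekly answers to one label per worker: "Overall PPE usage will be defined as the following from multiple weekly surveys being considered as above". In the mapping table that follows, a worker is *Yes always* only if that is the sole answer in all surveys considered. *No* needs the same unanimity, and every mixture is *Yes not always*.

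The surveys considered differ by group:

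- **Infected at entry:** the baseline survey only.
- **Infected at follow-up:** the whole follow-up available in the data cut. In addition, "overall PPE usage in the 2 or 4 weeks (TBD) prior to COVID-19 infection date will be described".
- **Never infected:** the whole follow-up, and additionally the same undecided 2 or 4 weeks counted back from the data cut date.

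Follow-up is limited: "The HCWs will be followed up for 12 weeks upon enrollment in the study". Section 6.3.8 sets no minimum number of surveys and no rule for missed weeks, although Protocol 8.9 expects some workers not to complete every survey. The section refers to Table 8.2.9, which sets the three groups side by side but is titled as PPE usage at baseline.

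In the model (SAP 6.4.1, Table 5.4.1), mask, gown, eye protection and glove use are time-varying covariates. The note to that table adds: "The necessity to create composite variables or collapse categories within variables will be determined upon the completion of the descriptive analyses".

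**The concern.** A label that needs a perfect record becomes harder to earn with each further survey. Two groups with identical weekly behaviour get different PPE distributions if one has fewer surveys counted. A worker infected in weeks 1 to 3 cannot have four weekly surveys in a 4-week look-back, whereas a never-infected worker can. The shorter record is more often *Yes always*, which works against seeing any protection. The middle category also discriminates poorly: one lapse in 12 weeks, and eleven weeks of *No* with one of *Yes always*, receive the same label.

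PPE is the first factor named in the second secondary objective. The stacked bar charts in 6.3.8 show only yes or no, so this summary is where consistent and inconsistent use are compared by infection status.

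**Working it through.** **Plan's own figure.** The PPE rule has none. The only design figure is in SAP section 5: "A total of N=10,000 allows for 80% power to identify an effect size of Relative Risk = 0.78". With 2,000 unexposed and 8,000 exposed workers, events = 2,000 × 0.10 + 8,000 × 0.078 = 824. Reading the relative risk as a hazard ratio, Schoenfeld's formula gives z = √(824 × 0.2 × 0.8) × |ln 0.78| − 1.96 = 0.89, which is 81.4% power. The figure is reproduced, and the point does not rest on it. Only the 10% risk from that section is borrowed below.

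**Assumptions (not in the documents).**

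- 90% of worker-weeks are *Yes always*.
- The weekly hazard is 0.0088 in weeks that are not *always*, so the 12-week risk is 1 − (1 − 0.0088)^12 ≈ 10.1%.
- An *always* week has hazard ratio 1 or 0.7.
- Every survey is answered, and each look-back includes the survey for the infection week.
- Never-infected workers have a full window.

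**Step 1: record length alone.** With weekly probability p and k surveys, P(*Yes always*) = p^k.

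| p | 1 survey | 4 surveys | 12 surveys |
|---|---|---|---|
| 0.80 | 80% | 41% | 7% |
| 0.90 | 90% | 66% | 28% |
| 0.95 | 95% | 81% | 54% |

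If adherence varies between workers (beta distribution, mean 0.9, concentration 10, 5 or 2), twelve surveys give 43%, 51% or 64%.

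**Step 2: 4-week look-back, no PPE effect, p = 0.9.** Infections are spread almost evenly over 12 weeks, so cases have 1, 2, 3 and then (nine times) 4 surveys.

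- Cases: (0.9 + 0.81 + 0.729 + 9 × 0.6561)/12 = 0.695.
- Uninfected: 0.9^4 = 0.656.
- Odds ratio: (0.695/0.305)/(0.656/0.344) ≈ 1.20, where 1.00 is correct.

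**Step 3: 4-week look-back, true hazard ratio 0.7.** In the infection week, P(*always* given infected) = 0.63/(0.63 + 0.10) = 0.863. Earlier weeks stay close to 0.9.

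- Cases: 0.863 × (1 + 0.9 + 0.81 + 9 × 0.729)/12 = 0.667.
- Odds ratio: (0.667/0.333)/(0.656/0.344) ≈ 1.05.
- For comparison, the infection-week survey alone gives (0.63/0.10)/(0.9/0.1) = 0.70, the true value.

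**Step 4: 2-week look-back.**

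- No effect: cases (0.9 + 11 × 0.81)/12 = 0.8175 against 0.81, odds ratio 1.05.
- Hazard ratio 0.7: cases 0.863 × (1 + 11 × 0.9)/12 = 0.784, odds ratio 0.85.

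**Step 5: whole follow-up, 12 surveys in both groups, hazard ratio 0.7.** Cases 0.863 × 0.9^11 = 0.271; uninfected 0.9^12 = 0.282; odds ratio 0.94. With no effect it is about 1, because the counts are equal.

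**Step 6: allowing adherence to vary between workers.** Simulation with constant or beta-distributed adherence gives these odds ratios for *Yes always*, infected at follow-up versus uninfected:

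| Window | No effect | True hazard ratio 0.7 |
|---|---|---|
| 4 weeks | about 1.13–1.20 | about 0.94–1.05 |
| 2 weeks | about 1.04–1.06 | about 0.81–0.85 |
| Whole follow-up, equal counts | about 1 (0.98–1.02) | about 0.90–0.94 |

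A wider set of simulations (mean adherence 0.8 or 0.9, several within-worker correlations) scored PPE by person-week at risk. That returned rate ratios of 0.97–1.02 for a true value of 1 and 0.67–0.71 for 0.7. The information is in the weekly data; the collapse loses it.

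**The case against.** The best defence is that this is one descriptive summary and the inferential work does not use it. The Cox model lists the four PPE types as time-varying, and the risk-factor analysis in SAP 6.5 tests covariates of that model. The note to Table 5.4.1 concerns composites and collapsed categories; nothing says the per-person label enters the model. This stands. A reader might infer that the PPE hazard ratio is biased, but that would follow only if the label were carried in.

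A reader might also infer that the rule reverses a PPE effect and makes PPE look harmful. The documents do not support that for follow-up cases against uninfected workers. The main summary does not stop at infection, so with equal response the counts are equal and the result is dilution. Reversal needs survey counts that differ by infection status. For example, if response fell from 80% to 40% after infection, a true hazard ratio of 0.5 would give an odds ratio of 0.72 to 1.19 depending on adherence. The documents give no response rates.

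A third tempting reading sets entry cases with one survey (90% *Yes always*) against never-infected workers with twelve (28% to 64%). The baseline item covers use since first contact with COVID-19 patients, so an earlier lapse should already appear in it. That gap is at most an upper bound.

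Finally, the direction of the imbalance in the look-back is not fixed. The never-infected window ends at the data cut, and workers who finished their 12 weeks earlier may have few or no surveys in it. This is fair, but it makes the comparison less interpretable rather than safer.

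**Conclusion.** The point holds for the description in SAP 6.3.8. The unanimity rule makes the label depend on the number of surveys counted and hides how often lapses occurred. Under the stated assumptions, a true weekly hazard ratio of 0.7 is largely masked in the 4-week look-back and diluted, in the right direction, over the whole follow-up. The 2-week look-back is nearly free of the count artefact, but the SAP has not chosen it, so the result depends on an open setting.

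The sizes rest on assumed adherence, full response and a full window for the uninfected. The dependence on survey count is more general: it is present whenever weekly use is below 100% and workers' answers vary from week to week. This is a cheap improvement, not a threat to the primary analysis.

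**What to change.** - Replace the mapping table in 6.3.8 with each worker's proportion of surveyed weeks reported as *Yes always*, *Yes not always* and *No*, for each PPE type. Treat the count of PPE types the same way.
- Report the number of surveys answered by group.
- Compare follow-up cases with uninfected workers over windows holding the same number of surveys, anchored at comparable study weeks and not at the data cut date. Settle the 2- or 4-week choice in advance. Matched risk-set sampling is optional.
- Show entry cases only against baseline responses for all groups, and reconcile the title of Table 8.2.9 with 6.3.8.
- State that the collapsed label will not be used in the Cox model.

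The cost is SAP wording and reprogramming of one derived variable from data already collected. The drawback is a table of proportions in place of three simple categories.

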6.3.9 COVID-19 symptoms

The distribution of COVID-19 symptoms will be displayed for the following time periods after first indication of symptoms:

- Symptoms at any time on or after first symptoms seen for the HCW
- Symptoms within 1 week after first symptoms seen for the HCW
- Symptoms within 1-2 weeks after first symptoms seen for the HCW
- Symptoms within 2-4 weeks after first symptoms seen for the HCW
- Symptoms >4 weeks after first symptoms seen for the HCW

A summary of the proportion of HCWs that had at least one symptom, at least two symptoms, at least three symptoms will also be displayed within these time periods. A histogram will be produced where the bins along the x-axis are the number of unique symptoms each HCW reports on their survey. This descriptive analysis will aid in determining which symptoms or group of symptoms will be considered for diagnosing HCWs as being COVID-19 infected.

6.4 Primary analysis

6.4.1 Frailty model: mixed effect Cox regression

For the time to COVID-19 infection outcome, both crude and adjusted hazards ratios will be estimated for time to COVID-19 infection with respect to prophylaxis use. The primary objective of this analysis is to assess the association between prophylactic treatments and the reduced risk of SARS-CoV-2 infection in HCWs caring for COVID-19 patients. A mixed effect Cox regression model (ie. frailty model) will be used to estimate adjusted hazard ratios. This method will allow the utilization of both the repeated measures gathered from each HCWs surveys, as well as the incorporation of time-varying covariates of interest such as PPE usage and COVID-19 exposure. Each subject will be included as a random effect. Both time-fixed and time-varying covariates will be included in the model. Covariates will be assessed using a univariate model, any covariates with a p-value less than 0.20 will be included in a multivariate model. A backward stepwise process will then be completed, where the covariates with largest p-value are removed one at a time until all covariates that remain are significant at the 0.10 level. The time-fixed covariates, healthcare facility and country will be included in the model regardless of their significance level. Including the healthcare facility and country covariates will make each healthcare worker's COVID-19 outcome conditionally independent on the background COVID-19 incidence occurring within each subject's healthcare facility and country. A list of additional covariates to be considered can be found in Table 5.4.1. For each subject in the control group, the index date (ie. time of first known exposure to COVID-19 patients) will be used as time zero. For HCWs that are treated with prophylaxis at any time their index date will be 7 days after initiation of treatment. Having an index date near treatment initiation will prevent the introduction of survivorship bias into the analysis.

Table 5.4.1 Model Covariates

Time-fixed/Time-varying Covariate	Covariate Name
Time-fixed Covariates	Healthcare facility, Country, Age, Biological Gender, BMI, Smoking status, Ethnicity, Blood type, Primary work location, Type of healthcare worker, Medical history

Time-varying Covariates	Others in household exposed to COVID-19 infected individuals, Others in household showing symptoms of COVID-19, Others in household diagnosed with COVID-19, Number of COVID-19 infected patients exposed to, Direct care to COVID-19 patients, Face-to-face contact of COVID-19 patients, Present when aerosol generating procedures performed, Mask usage, Gown usage, Eye protection usage, Glove usage
-------------------------	--

Note: The necessity to create composite variables or collapse categories within variables will be determined upon the completion of the descriptive analyses. A correlation analysis will be completed to assess the level of correlation between variables, if a high level of correlation is found only one of the variables will be included as a covariate in the models.

A Cox model with mixed effects can be formulated as $h_i(t) = h_0(t) \exp(\mathbf{X}_i B + \alpha_j)$, where α_j denotes the random effect associated with the j -th cluster. The random effect can be thought of as a random intercept that modifies the linear predictor, while the shared frailty term has a multiplicative effect on the baseline hazard function: $h_i(t) = h_0(t) \exp(\alpha_j) \exp(\mathbf{X}_j B)^3$.

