8.7.4 Primary Analysis

A standard pharmaco-epidemiological inferential analysis will be conducted treating the registry data as a cohort with dynamic exposure to both prophylactic treatment and to COVID-19 infected patients and adjusting for potential confounding.

Both crude and adjusted hazards ratios will be estimated for prophylactic regimens of interest and any observed impact on the risk of infection among HCWs based on all statistical inferential models will be reported.

Outcomes will be adjudicated to exposure time based on prior decision rules agreed with the SAC. Hazards for each subject-week will be compared and adjusted for exposure to prophylaxis over time, exposure to COVID-19 positive patients over time and to other covariates, accounting for subject-level clusters. Repeated time-to-event analyses with competing risk will be carried out.

Handling of missing data and unexplained drop-outs will be discussed with the SAC. Interaction terms to be considered will also be discussed with the SAC and clinicians.

Matching or other balancing methods such as estimated propensity score matching, inverse probability weighting or marginal structural methods, or alternative methods, will be considered to potentially address the identified biases and allow for evaluation of association.

In case the number of infection cases is lower than anticipated to allow for such analyses, matched case-control analyses will also be considered.

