Appendix 3: List of Prophylactic Treatments

Select ALL that apply

1. Chloroquine - specify dose and interval
2. Hydroxychloroquine - specify dose and interval
3. Azithromycin - specify dose and interval
4. Lopinavir/ritonavir - specify dose and interval
5. Ivermectin - specify dose and interval
6. Other 1 – specify therapeutic, dose and interval
7. Other 2 – specify therapeutic, dose and interval
8. Other 3 – specify therapeutic, dose and interval

Signature Page for VV-TMF-757477 v0.1

Reason for signing: Approved	Name: [name] Role: Sponsor Date of signature: 17-Jun-2021 16:41:02 GMT+0000
------------------------------	---

Signature Page for VV-TMF-757477 v0.1

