6.3 Descriptive analyses

Prior to implementing the analysis to address the primary objectives of the study, descriptive analyses will be carried out to understand the main features and patterns in the population and in the data collected. Study population characteristics will be tabulated at index date.

WHO Ordinal Scale for Clinical Improvement (see Appendix 1) scores distribution over time will be displayed. Kaplan-Meier estimates will be calculated, and curves plotted for each time-to-event outcome.

The observed incidence weekly rates of PCR-confirmed or symptomatic COVID-19 and of COVID-19-related hospitalizations and deaths will be tabulated over weeks by facilities and compared according to

prophylactic treatment use (yes/no; by treatment, subject to sufficient sample size; and by pre- and post-exposure (to COVID-19 patients) use, subject to sufficient sample size).

Applications of estimated propensity scores will be employed to explore differences between HCWs' profiles exposed versus non-exposed to potential prophylactic treatments. Propensity scores will be estimated for receipt of potential prophylactic treatments based on key covariates of interest for the HCWs' profiles (age, gender, race, type of HCW, BMI, smoking status, medical history). Estimated propensity score distributions will be displayed over weeks and a concordance analysis performed to detect any trend over time.

Stratified pooled analyses at country level will also be displayed.

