6.7 Sensitivity analyses

The following sensitivity analyses will be performed for the primary analysis:

- According to the four definitions of the primary outcome of COVID-19 infection (ie. positive test only, symptoms only, clinical diagnosis only, hospitalized only)
- Imputing unexplained drop-outs as events. Healthcare workers that are lost to follow-up will be treated as positive for COVID-19 infection.

In the event that the estimated hazard ratio of treated versus control in the primary analysis is 0.8 or less, but no statistical significance can be established due to a small sample size, an alternative approach such as empirical Bayesian meta-analysis will be employed to leverage published local data.

7 Minimization of study bias

As this is an observational study based on self-reported information from HCWs, there are several potential limitations and biases that will need to be considered, as follows:

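### SAP 6.4.1 does not define the prophylaxis exposure by drug and plans no adjusted regimen-level hazard ratios, although current protocol 8.7.4 commits to them

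*SAP*

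**What the plan says.** Protocol 8.7.4, in the current version 1.1, states: "Both crude and adjusted hazards ratios will be estimated for prophylactic regimens of interest". The protocol abstract says the same.

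SAP 6.4.1 states that "both crude and adjusted hazards ratios will be estimated for time to COVID-19 infection with respect to prophylaxis use". It sets a control group against workers who take prophylaxis at any time. Table 5.4.1 lists the covariates and contains no drug term. SAP 6.7 then refers to the "estimated hazard ratio of treated versus control in the primary analysis", in the singular. Sections 6.5, 6.6 and 6.7 list no hazard ratio for an individual drug.

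Prophylaxis covers chloroquine, hydroxychloroquine, azithromycin, lopinavir/ritonavir, ivermectin and others (SAP 3.5.2). Protocol Appendix 3 lets a worker tick several entries and offers three free-text lines, the first being "Other 1 – specify therapeutic, dose and interval".

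Individual drugs do appear in the descriptive part of the SAP. Section 6.3 compares weekly incidence rates "by treatment, subject to sufficient sample size". Section 6.3.7 plans bar charts by drug if numbers permit, and Table 8.2.8 counts users of each drug.

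The sample size (SAP section 5, identical in protocol 8.7.7) "assumes that 20% of the study population are non-exposed to potential prophylactic treatments" and concludes: "A total of N=10,000 allows for 80% power to identify an effect size of Relative Risk = 0.78". SAP section 1 says that the plan is based on protocol version 1.0.

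**The concern.** The registry is meant to inform policy on the use of particular drugs. An any-prophylaxis hazard ratio is roughly an average over unrelated agents, weighted by how popular each was at the sites. A value near 1 would not show that every drug lacks an association, and a value below 1 could not be credited to any one of them. If only one drug is associated with lower risk, the rest of the mix pulls the pooled estimate towards 1.

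The unadjusted rates in SAP 6.3 cannot fill the gap. Protocol 8.9 and SAP 7.5 both warn of confounding by indication and channelling, which is why the protocol asks for adjusted estimates. An analyst who followed the SAP as written would probably not deliver what the current protocol commits to.

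**Working it through.** **Inputs from the documents.** N = 10,000, of whom 20% (2,000) are untreated and 8,000 treated; risk in the untreated 10%; target relative risk (RR) 0.78; stated power 80% (SAP section 5). For the test level, SAP 6.1 says: "All statistical tests will be two-sided and at 5% level of significance".

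**Assumed.** The share s of the 8,000 treated workers who use the one active drug, because the documents give no shares. All other prophylaxis is taken as inert (RR 1), users of the active drug take only that drug, and RR is used as the hazard ratio.

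**Formula (Schoenfeld).** Power = Φ(|ln HR| × √[D × p(1 − p)] − z), where D is the number of events, p the untreated fraction, and z = 1.960 at two-sided 0.05. Only rejections in the protective direction are counted, so a value can fall slightly below 5%.

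**Step 1: the plan's own figure.** D = 2,000 × 0.10 + 8,000 × 0.078 = 824 and p(1 − p) = 0.16. Power = Φ(0.2485 × √131.84 − 1.960) = Φ(0.893) = 81.4%. The stated 80% is reproduced, as the power of one contrast in which all 8,000 treated workers share RR 0.78.

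**Step 2: only one drug carries the effect.** Pooled RR = 1 − s × (1 − 0.78). The drug's own contrast sets its 8,000 × s users against the same 2,000 untreated.

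Worked line for s = 20%:
- Pooled RR = 1 − 0.20 × 0.22 = 0.956 and D = 200 + 800 × 0.956 = 964.8. Power = Φ(0.0450 × √154.4 − 1.960) = 8.1%.
- Own contrast: 1,600 users, D = 200 + 124.8 = 324.8, p = 2,000/3,600, p(1 − p) = 0.2469. Power = Φ(0.2485 × √80.2 − 1.960) = 60.5%.

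| Share of treated | Pooled RR | Pooled power | Own-contrast power, alpha 0.05 | Own-contrast power, alpha 0.01 |
|---|---|---|---|---|
| 10% | 0.978 | 4.6% | 44.4% | 22.4% |
| 20% | 0.956 | 8.1% | 60.5% | 36.3% |
| 40% | 0.912 | 20.1% | 72.7% | 49.5% |

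Alpha 0.01 is a Bonferroni split over five regimens. A split over six (0.05/6) gives 20.6%, 34.0% and 47.0%.

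**Step 3: the limit of dilution.** A drug that prevented every infection would give a pooled RR of 1 − s. Below a share of 22% it could not bring the pooled RR down to 0.78.

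**Step 4: robustness.**
- A pooled two-proportion test gives 87.7% for the plan's own case, so it reproduces the stated 80% less well. It gives pooled power of 4.9%, 8.9% and 23.3%, and own-contrast power of 43.5%, 63.1% and 77.8%. The pattern is the same.
- With 75% treated, the figure in protocol 8.2.3, power for RR 0.78 in the whole treated group is 87.5%. The allocation does not drive the result.
- For a stronger drug with RR 0.60, pooled power is 17% at a 20% share and 54% at 40%. Own-contrast power is 99% or more in both cases.
- For RR 0.50, pooled power is about 9%, 25% and 73% at shares of 10%, 20% and 40%.

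**Step 5: what the regimen contrasts can detect.** With 80% power at alpha 0.05, the detectable RR is 0.68, 0.73 and 0.76 at shares of 10%, 20% and 40%.

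**The case against.** Four points can be made for the SAP.

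- **The pooled contrast is the design basis.** Both documents size the study on treated versus untreated, so a pooled hazard ratio is the powered analysis. This stands, and it is the reason to keep that estimate.
- **The SAP never writes out a pooled term.** Section 6.4.1 also states its objective for treatments in the plural, and 6.3.7 distinguishes any use from individual drugs when it means to. A reader might infer that the SAP expressly counts a worker who took only an unlisted product in the same way as a user of a listed drug. No sentence says so. It is the likelier reading because nothing excludes those workers and the text speaks of one treated group and one control group. The defect that can be shown is an undefined exposure variable.
- **The SAP predates the wording.** A reader might infer that the SAP deliberately cut the protocol's regimen-level estimates down to one. The documents do not support that. The amendment log shows that the regimen wording entered 8.7.4 with version 1.1, while the SAP follows version 1.0. Similar wording may already have stood elsewhere in version 1.0, which is not available. This explains the mismatch but does not remove it.
- **By-drug rates are compared.** They are, in SAP 6.3, but without adjustment and only if numbers allow.

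Regimen-level estimates also have costs: less precision, more comparisons, and a need for rules on switching. These bear on the form of the fix, not on whether it is needed.

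**Conclusion.** The SAP is out of line with the current protocol. It leaves the exposure term undefined, points to a single any-prophylaxis hazard ratio, and plans no adjusted hazard ratio by regimen.

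Under the stated assumptions the dilution is large for a drug with a modest share. At a 20% share and RR 0.78, power is about 8% pooled against about 60% for the drug's own contrast. The size depends on drug shares that the documents do not give and on the other drugs being inert.

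It would go too far to say that the pooled analysis must miss an active drug. A strong association in a widely used drug would usually show, as the 73% at RR 0.50 and a 40% share illustrates. Nor would regimen-level estimates show that a drug works: the objective is association, and this is an observational registry. The change is inexpensive and should be made before analysis.

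**What to change.** 1. Define the exposure variable in SAP 6.4.1 and update the SAP to protocol version 1.1.
2. Keep the pooled any-prophylaxis hazard ratio.
3. Add adjusted hazard ratios with 95% confidence intervals against no prophylaxis for each regimen: chloroquine/hydroxychloroquine, azithromycin, ivermectin, lopinavir/ritonavir, combinations, and Other only.
4. Code regimen as time-varying, with a stated rule that assigns switches and add-ons, and say which drug's initiation sets time zero.
5. Set a minimum number of users or events for a regimen to be modelled.
6. Either state a multiplicity rule or label the regimen results as estimation without formal testing. Six independent tests at 0.05 carry a family-wise error of 1 − 0.95⁶ = 26.5%.
7. As a sensitivity analysis, repeat the pooled hazard ratio without Other-only users.

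Drug names and start and stop dates are already collected, so the cost is SAP text and derivation rules. The downside is wider intervals. By Schoenfeld, power for RR 0.78 in a single regimen stays below 80% at every share examined (29% to 77% at alpha 0.05, for shares of 5% to 60%). The SAP should say so.
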